### 16.2 Statistical Design

#### 16.21 Decision Rules

The primary endpoint of this trial is the proportion of patients treated with F-DOPA-PET guided radiotherapy who are alive and have not progressed within 3 months. A success will be a patient who is alive and without evidence of progressive disease within 3 months from registration. Median PFS after bevacizumab failure ranges between 1-2 months.[17, 34] Thus, the largest success proportion where the proposed treatment would be considered ineffective in this population is 20%. The following Simon's Optimum design uses 20 patients to test the null hypothesis that the proportion of successes is at most 20% with an overall significance level (alpha) of 0.186, and a power of 85.9% to detect a true success proportion of 40%.

16.22 After 10 evaluable patients are accrued to this study and followed for at least 3 months, if 2 or more successes are alive and progression-free at 3 months, the results will wait until conclusion of the study. If 1 or fewer patients are alive without evidence of progression at 3 months, the study will be stopped and the treatment will be deemed ineffective in this population.

16.23 After 20 evaluable patients are accrued to this study and followed for at least 3 months, if 6 or more successes are observed we may recommend further testing of this regimen in subsequent studies in this patient population.

16.24 We will not suspend accrual between stages to allow the first 20 patients to become evaluable, unless undue toxicity is observed.

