##### 16.71 Primary Endpoint:

16.711 Definition: the primary endpoint of this trial is proportion of patients experiencing progression-free survival at 3 months. All patients meeting eligibility criteria who have a signed consent form on record and who have begun F-DOPA-guided reirradiation treatment at Mayo Clinic will be evaluable for the endpoint. All eligible patients will be followed until death or a maximum of 4 years. Time to disease progression is defined as the time from study registration to the earliest date documenting disease progression. If a patient dies without evidence of disease

progression, the patient will be censored on the last date the tumor was evaluated. If a patient is declared to be a major treatment violation, the patient will be censored on the date the treatment violation was declared to have occurred. In the case of a patient starting treatment and then never returning for any evaluation, the patient will be censored for progression on the last day of therapy.

16.712 Estimation: the proportion of successes will be estimated by the number of successes divided by the total number of evaluable patients. Confidence intervals for the true success proportion will be calculated according to the approach of Duffy and Santner.[37]

16.713 Over Accrual: if more than the target number of patients are accrued, the additional patients will not be used for evaluation of stopping rules or in any decision making process. They will be included in the final point estimates and confidence limits.

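### Section 16.711 puts time-to-progression censoring inside a binary 3-month endpoint and leaves a patient alive without a tumor assessment with no clear score

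*Combined protocol and SAP*

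**What the plan says.** **The endpoint is a count.** Section 16.21: "A success will be a patient who is alive and without evidence of progressive disease within 3 months from registration". Section 16.22 stops the trial after 10 patients on this rule: "If 1 or fewer patients are alive without evidence of progression at 3 months". Section 16.23 needs 6 or more successes of 20 before further testing may be recommended. Section 16.5 takes the number of successes as binomial, and under Section 16.712 "the proportion of successes will be estimated by the number of successes divided by the total number of evaluable patients".

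**The denominator.** Section 16.711 says that eligible, consented patients who have begun the guided "reirradiation treatment at Mayo Clinic will be evaluable for the endpoint". Section 13.2 makes non-evaluable only those who get no radiation treatment or get it elsewhere.

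**The censoring rules.** The same Section 16.711 defines time to progression from registration and censors three groups:

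- death without progression: "the patient will be censored on the last date the tumor was evaluated";
- violations: "If a patient is declared to be a major treatment violation, the patient will be censored" at the date of the violation;
- patients who start treatment and then leave: "never returning for any evaluation, the patient will be censored for progression on the last day of therapy".

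**Related text.** Section 11.414 counts failure to return as progression when the reason is death or deterioration. Section 16.3 adds 2 places to the 20, and major treatment violation is among the reasons. Section 16.713 says of patients beyond the target that "additional patients will not be used for evaluation of stopping rules or in any decision making process". Section 13.4 sends patients who withdraw from scans to event monitoring.

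**The concern.** A count has no place for a censored observation. Each patient in the denominator is a success or is not. Section 16.711 does not say how a patient censored before 3 months enters the fraction, and no time-to-progression analysis is planned that would use the censoring. Kaplan-Meier is named only for survival, in Section 16.81.

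Three groups are affected, to different degrees:

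1. **Deaths, and non-return through death or deterioration.** The censoring sentences conflict with Sections 16.21, 16.22 and 11.414.
2. **Patients alive at 3 months without a tumor assessment.** Two readings give opposite treatment, and nothing in the text chooses between them.
3. **Treated major violators.** One part of the text keeps them in the denominator; another censors them and provides spare places.

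One patient can settle the result. With 5 clear successes and one unassessed patient, the outcome is 5/20 = 25% or 5/19 = 26.3%, with the cut-off of 6 not met, or 6/20 = 30%, with it met. If the scoring rule is left until the data are known, it can be chosen with the answer in view.

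**Working it through.** **Inputs from the plan (Sections 16.21 to 16.23).** First stage 10 patients, stop at 1 or fewer successes; final 20 patients, positive at 6 or more; null 20%, alternative 40%; stated alpha 0.186 and power 85.9%.

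**Step 1: the plan's own figures.** Let X1 and X2 be the successes in the first and second ten, each Bin(10, p). Then

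P(positive) = sum over x from 2 to 10 of P(X1 = x) × P(X2 ≥ 6 − x).

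This gives 0.1863 at p = 0.20 and 0.8586 at p = 0.40, so both stated figures reproduce. The chance of stopping at the first stage when p = 0.20 is P(X1 ≤ 1) = 0.376.

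**Step 2: patients without a 3-month assessment.** Assume K of the 20 are unassessed, at random positions and unrelated to outcome. The documents give no rate, so K = 1 and K = 2 are illustrations. The chance that j of them fall in the first ten is C(10, j) × C(10, K − j) / C(20, K). The assessed patients contribute X1 ~ Bin(10 − j, p) and X2 ~ Bin(10 − K + j, p).

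- Scored as successes: continue if X1 + j ≥ 2; positive if X1 + X2 + K ≥ 6.
- Scored as non-successes: continue if X1 ≥ 2; positive if X1 + X2 ≥ 6.

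| Unassessed of 20 | Scored as | Type I error (p = 0.20) | First-stage stop (p = 0.20) | Power (p = 0.40) |
|---|---|---|---|---|
| 0 | – | 0.186 | 0.376 | 0.859 |
| 1 | success | 0.312 | 0.255 | – |
| 2 | success | 0.479 | 0.160 | – |
| 1 | non-success | 0.155 | – | 0.819 |
| 2 | non-success | 0.126 | – | 0.772 |

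The two readings move the error rate in opposite directions, and scoring as success is the larger distortion.

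**Step 3: treated major violators, if they are removed.** The numbers removed are again assumed.

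- Removed regardless of outcome and fully replaced: still 20 independent patients, so 0.186 and 0.859 are unchanged.
- Removed regardless of outcome from the second ten and not replaced, cut-off still 6: n = 19 gives 0.157 and power 0.826; n = 18 gives 0.130 and 0.784.
- Removed more often when they are failures (failures 10%, successes 5%), replaced within the cap of 22: type I error 0.199.
- Extreme case, one or two true failures removed and replaced: total successes S ~ Bin(20 + D, 0.20), with first-stage successes hypergeometric among the 20 kept. D = 1 gives 0.220 and D = 2 gives 0.255.

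**Step 4: deaths.** No arithmetic is needed. A patient who dies before 3 months is not alive (Section 16.21), is evaluable if eligible and treated (Section 16.711), and so is in the denominator but not the numerator (Section 16.712).

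**The case against.** The strongest reply is that the censoring sentences follow a definition of time to progression and belong to that variable. Censoring a time does not change a binary score or remove anyone from a denominator. For deaths this stands: Section 16.21, the evaluable definition and Section 16.712 together give non-success. A reader might infer that the plan drops early deaths or counts them as progression-free. The documents do not support that; the defect there is contradictory text. For unassessed patients the reply does not help, because letting Section 16.21 govern produces the success reading.

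Second, Sections 16.22, 16.23 and 16.7 apply the counts after 3 months of follow-up, which makes it less natural to score someone lost at 1 month as a success. That is fair, but follow-up is not defined as a tumor assessment. Section 4.0 schedules MRI at 1 and 3 months after radiotherapy and Section 3.18 requires willingness to return, so missing scans may be few. One is enough to matter.

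Third, a reader might infer that progression goes unrecorded in event monitoring. It does not: Section 18.1 has forms due at progression, and Section 11.416 names the Event Monitoring Form for its date. What is absent is a scheduled scan to find it.

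Fourth, the violator branch is weak. Sections 16.711 and 13.2 already make treated violators evaluable. Only the censoring sentence and the accrual allowance in Section 16.3 point the other way, and that allowance is not an analysis rule. A reader might infer that removing violators must inflate the error rate; Step 3 shows that this needs removal and replacement tilted sufficiently towards failures.

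Last, Section 16.23 says only that further testing may be recommended, so the upper cut-off is not a binding decision. The first-stage stop is worded as binding.

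**Conclusion.** The point holds. The primary-endpoint definition contains censoring rules that the count cannot use and that no planned analysis needs. For deaths, and for non-return through death or deterioration, they contradict other sections but leave the score determinable. For a patient alive without a 3-month tumor assessment, the text supports a literal success or a censored observation and does not choose. With one or two such patients of 20, the success reading takes type I error from 0.186 to 0.312 or 0.479.

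These figures assume the number unassessed and that missingness is unrelated to outcome. They show sensitivity; they do not predict what the trial will see. A reader might infer that the stated alpha and power are wrong. They are not: both reproduce exactly when each of the 20 patients is scored on true status.

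Confidence is high for the contradiction over deaths and for the missing rule on unassessed patients, and moderate for violators, where the inconsistency is smaller. It should be corrected before outcomes are reviewed.

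**What to change.** State in Section 16.711, for the 3-month endpoint:

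1. Every eligible, consented patient who began the guided reirradiation stays in the denominator.
2. Death from any cause by 3 months, and non-return that meets Section 11.414, are non-successes.
3. A success requires a tumor assessment showing no progression in a named window around 3 months. The window has to be named because Section 4.0 times the 3-month MRI from the end of radiotherapy, while Section 16.21 counts from registration.
4. Patients with unknown status are non-successes, with a sensitivity analysis that excludes them.
5. Treated major violators are scored on observed status. Align Section 16.3 so that its spare places cover ineligible or untreated patients.

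Move the three censoring sentences to a separately named time-to-progression analysis, or delete them. Other scoring choices under items 4 and 5 are defensible if fixed in advance.

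The cost is a few sentences, with no change to sample size or cut-offs. Item 4 loses power if assessments are missing: 0.859 falls to 0.819 with one unknown and 0.772 with two, under the assumptions of Step 2. The reported 3-month rate may be slightly less favourable.

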## 16.8 Definitions and Analysis of Secondary and Correlative Endpoints

Subgroup analyses will be included as appropriate for these secondary endpoints to assess known prognostic factors.

16.81 Overall Survival: compare overall survival (OS) at 12 months for patients after radiation therapy targeting volumes designed using F-DOPA in addition to MRI contrast enhancement with historical controls. Survival time will be determined from the time of initial diagnosis to death from any cause. Survival from reirradiation will be determined from the time of study registration to the time of death from any cause. The distributions of the survival time will be estimated using the Kaplan-Meier method.[38]

16.82 Volumetric Comparison: to differences in the F-DOPA-PET avid region with abnormalities on MRI, the treating radiation oncologists will first define treatment volumes for GTV\_MRI using the T1-post contrast MRI scans while blinded to the PET study. A volume named T2\_FLAIR\_NCET will be defined by outlining T2 hyperintensity on T2 FLAIR MRI sequences. Then the PET study will be fused with the contouring software to allow automated contouring of GTV\_PET defined by the T/N ratio > 2.0 (and T/N > 1.5). These contours will be reviewed by the treating radiation oncologist and then expanded as noted above. The volume of overlap and non-overlap between the GTV\_MRI, T2\_FLAIR\_NCET and GTV\_PET will be calculated. Paired t-test statistical analysis will be performed to determine if any differences exist and the level of statistical significance between treatment volumes defined by MRI only and the treatment volumes defined by both PET and MRI. The analysis of volumes from 20 patients will have 80% power to detect differences in volumes with an effect size of 0.63 using a paired t-test with 0.05 two-sided significance level. Alternate metrics for comparison will also be assessed including spatial overlap, distance, correlations, and 3D shape comparisons.

- 16.83 **Patterns of Failure:** observe patterns of failure after reirradiation using  $^{18}\text{F}$ -DOPA-PET to guide treatment volumes. The MRI scan indicating progressive disease will be fused with our treatment planning scan and the region of progression will be contoured by an investigator blinded to the GTV\_MRI, T2\_FLAIR\_NCET, GTV\_PET, PTV\_high, and isodose lines. A volumetric analysis will then be performed to define the doses delivered to the absolute and relative volume of the region where recurrence is defined.
- 16.84 **Adverse Events:** determine acute and late toxicity after radiotherapy treatment using  $^{18}\text{F}$ -DOPA-PET to delineate treatment volumes. The rate of acute and late treatment-related toxicities for recurrent high-grade glioma patients treated with  $^{18}\text{F}$ -DOPA-PET image-guided radiotherapy will be determined, with acute RT toxicities graded using Common Terminology Criteria for Adverse Events (CTCAE) version 4.0 (available at <http://ctep.cancer.gov>), and late toxicities reported using RTOG/EORTC late toxicity criteria.[39]
- 16.85 **Reoperation Rates:** determine the rate of reoperation for patients undergoing reirradiation for recurrent high-grade gliomas treated using  $^{18}\text{F}$ -DOPA-PET guided volumes. When available, pathologic information detailing the presence of necrosis and/or tumor progression will be recorded.
- 16.86 **Quality of Life:** estimate quality of life (QOL) after radiotherapy using  $^{18}\text{F}$ -DOPA-PET to establish treatment volumes. QOL will be evaluated using the MD Anderson Symptom Inventory Brain Tumor Module (MDASI-BT) and fatigue will be evaluated using the MD Anderson Brief Fatigue Inventory. These questionnaires will be administered at baseline and at each MRI evaluation up to 6 total evaluations to capture quality of life and correlate findings with clinical and radiographic progression. Analysis will include change percent from baseline using t-tests and generalized linear models to test for changes at each time point and non-zero slope.

16.9 **Data Safety Monitoring Plan**

The Study Chairs and the study statistician will review the study at least twice a year to identify accrual, adverse event, and any endpoint problems that might be developing. The Mayo Clinic Cancer Center (MCCC) Data Safety and Monitoring Board (DSMB) is responsible for reviewing the accrual and safety for this trial at least twice a year, based on reports provided by the MCCC Statistical Office.

- 16.91 **Adverse Event Stopping Rules:** As no reactions to  $^{18}\text{F}$ -DOPA have been reported within the institution, toxicity testing reported in the literature revealed no deleterious effects (section 0), and there have been no allergic reactions in all

patients accrued to date on multiple studies MC1078, MC1373, and MC1374, no reactions are anticipated. As such, if either of the two scenarios below occur, enrollment will be suspended so that details of each episode can be examined and a trial recommendation will be formulated and presented to the MCCC DSMB:

- At any point during the AE evaluation of the first 9 AE-evaluable patients, one or more patients is unable to complete PET scanning due to allergic reactions to the tracer.

Or, after 10 or more patients are evaluable for AEs, more than 10% of these patients are unable to complete PET scanning due to allergic reactions to the tracer.

There have been no reports in the literature of the occurrence of nephrogenic systemic fibrosis (NSF) in patients with normal renal function. Additionally, we will use the contrast agent gadobenate dimeglumine, which has been shown to have a high safety profile (lower incidence of NSF in patients with renal failure/insufficiency) compared with many other available Gd-based contrast agents. Therefore no reactions are anticipated. As such, if at any time a patient develops NSF enrollment will be suspended so that details of the episode can be examined and a trial recommendation will be formulated and presented to the MCCC DSMB.

Using the radiation treatment dosing, fractionation and normal tissue constraints outlined in Section 7 have been performed in several studies without significant adverse effects. While radiation-induced brain necrosis is rare, a cumulative normal brain dose of < 100 Gy in 2 Gy equivalents has been suggested as a constraint to minimize the risk of necrosis.[30] Two large studies reported no grade 3 or higher toxicity and no radionecrosis using the same dosing and fractionation as our protocol.[26, 27] In fact, studies using larger fraction sizes (5 Gy/fraction) reported very low rates of radionecrosis when keeping reirradiation doses under 40 Gy.[28, 29] However, tumor progression is expected in the majority of patients and commonly results in severe neurologic symptoms near the end of life. Both acute (available at <http://ctep.cancer.gov>) and late [39] toxicity will be monitored continuously as each patient is accrued and follow-up data are accumulated. If at any time, 1) 3 or more of the first 9 AE-evaluable patients; or, 2) after 10 or more patients are AE-evaluable, more than 30% experience any of the following adverse effects considered to be at least possibly related to radiation treatment up to and including the three-month timepoint; enrollment will be suspended so the details of each episode may be examined and a trial recommendation will be formulated and presented to the MCCC DSMB, adjusting the dose, fraction size or volumes as needed.

- Grade 3 or 4 irreversible CNS toxicity
- Grade 4 non-hematologic, non-CNS toxicity
- Any Grade 5 toxicity

Initial estimated Primary Completion Date: At study activation, this study will have been registered within the www.ClinicTrials.gov (CT.gov) website. The Primary and Secondary endpoints along with other required information for this study will be reported on CT.gov. For purposes of timing of the CT.gov results reporting, the initial estimated completion date of the primary endpoint of this study is 27 months after the study opens to accrual.

16.101 Definition of Primary-Endpoint Completion Date (PCD): The PCD is the date at which the last progression free patient has been followed for 3 months.

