### 2.3 Correlative Research

- 2.31 Compare volume of  $^{18}\text{F}$ -DOPA-PET uptake with MRI contrast enhancement and T2 FLAIR for patients undergoing re-irradiation for recurrent high-grade glioma
- 2.32 Evaluate patterns of failure after reirradiation in relation to pre-treatment MRI and  $^{18}\text{F}$ -DOPA-PET abnormalities

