7.41 Exploratory analysis for other T/N thresholds and SUV levels will be investigated

7.5 Radiation therapy

7.51 Target delineation

Following informed consent and co-registration of PET and MRI datasets with the planning CT acquired during standard CT simulation, the radiation oncologist will define the target volumes to use for radiation treatment planning.

7.52 Target delineation will be based on MRI and PET imaging, defining a gross tumor volume (GTV), clinical target volume (CTV), and planning target volume (PTV) as defined below. In the event that gross disease is multifocal on MRI or FDOPA-PET, contours do not need to be contiguous.

- 7.5121 GTV\_MRI = standard of care MRI contrast enhancement
- 7.5122 GTV\_PET = high signal PET disease
- 7.5123 GTV\_high = boolean of GTV\_MRI and GTV\_PET
- 7.5124 CTV\_high = GTV\_high
- 7.5125 PTV\_high = CTV\_high with a 0-2 mm expansion, based on the radiation oncologist’s clinical judgment

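### The only powered test of volumes in 16.82 compares nested volumes, so it cannot answer objective 2.31, which is otherwise covered only descriptively.

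*Combined protocol and SAP*

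**What the plan says.** Objective 2.31 is to compare the volume of PET "uptake with MRI contrast enhancement and T2 FLAIR for patients undergoing re-irradiation".

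Section 16.82 provides three contours: GTV_MRI (drawn blind to PET), T2_FLAIR_NCET and GTV_PET (at T/N above 2.0, and also above 1.5). Their overlap and non-overlap will be calculated. The only named test is a paired t-test of "treatment volumes defined by MRI only and the treatment volumes defined by both PET and MRI". The power statement follows directly: "The analysis of volumes from 20 patients will have 80% power" for an effect size of 0.63, "using a paired t-test with 0.05 two-sided significance level". The section closes with alternate metrics: spatial overlap, distance, correlations and shape.

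Section 7.52 defines GTV_high as the "boolean of GTV\_MRI and GTV\_PET", without saying whether this means union or intersection, and sets "CTV\_high = GTV\_high". The PTV adds 0-2 mm by judgment.

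Section 7.4 adds descriptive measures: union, intersection and discordant regions of the PET and MR volumes, and, for patients with PET uptake outside the MR volume, margin coverage and maximal distance.

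**The concern.** The objective sets PET uptake against two MRI abnormalities. The test sets MRI against MRI combined with PET. PET alone is in neither arm of the tested contrast, and FLAIR is in neither arm.

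The combined volume is also built from the MRI volume it is compared with, so the direction of the difference is known before any data exist. The risk is in the reporting. A small P value could be written up as showing that PET and MRI volumes differ in size, when it shows only that a union is larger, or an intersection smaller, than one of its parts.

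**Working it through.** **1. The plan's own figure.** Inputs from 16.82: n = 20, effect size 0.63 (mean paired difference over its SD), two-sided alpha 0.05.

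- Normal approximation: Φ(0.63 × √20 − 1.960) = Φ(0.857) = 80.4%. This reproduces the stated 80%.
- Exact noncentral t on 19 df: 76.2%. It reaches 80.4% at n = 22, and at n = 20 an effect size of 0.66 is needed for 80%.

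The stated power thus rests on the normal approximation. That is a side matter here; the main issue is which contrast it is attached to.

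**2. Nesting.** Let M = GTV_MRI and P = GTV_PET, and let |·| denote volume.

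- Union: |M ∪ P| − |M| = volume of P outside M, which is at least 0.
- Intersection: |M ∩ P| − |M| = −(volume of M outside P), which is at most 0.

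The sign is fixed whichever operator is meant. A mean of differences that all share one sign is zero only if every difference is zero. Because CTV_high equals GTV_high, the same holds at CTV level. At PTV level it holds only if both volumes receive the same expansion within the 0-2 mm allowed.

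**3. What significance requires.** With n = 20 the critical t is 2.093. Since t = √20 / CV, where CV is the SD of the differences over their mean, P < 0.05 needs only CV < √20 / 2.093 = 2.14. If k of 20 patients have the same added volume and the rest have none:

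- k = 3: mean 0.15, SD 0.366, t = 1.83, P = 0.083.
- k = 4: mean 0.20, SD 0.410, t = 2.18, P = 0.042.

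**4. How likely that is.** The documents give no mean, SD or frequency of PET volume outside MRI, so every input here is assumed: 20,000 simulated trials per scenario, n = 20, lognormal volumes with median 20 cc for both modalities, shared patient SD 0.8 on the log scale, modality SD 0.2-0.5, and overlap drawn from 50-90% of the smaller volume. In the remaining patients PET lies wholly inside MRI. The operator is taken as union.

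| Share of patients with PET outside MRI | Nested test, P < 0.05 |
|---|---|
| 100% | about 97-99% |
| 50% | 73-87% |
| 25% | 23-33% |
| 15% | 5-8% |

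A second model, with lognormal added volume of CV 0.5 to 3 and zero in the other patients, gives the same pattern: 100% down to 83% if all patients have added volume, 99% down to 52% if half do, and 61% down to 13% if a quarter do.

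**5. Nested against direct test.** Take equal mean volumes, overlap fixed at 50-95% of the smaller volume, and discordance in every patient. The direct PET vs MRI t-test rejects in about 5% of trials, as it should. The nested test rejects in 84-99% (union) or 97-99.9% (intersection). In these scenarios the nested P value carries no information about relative size.

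**The case against.** The documents answer part of this. Objective 2.31 says compare, not test. Overlap and non-overlap together give the size of each volume, so a reader will see whether PET is larger or smaller than enhancement or FLAIR. Section 7.4 adds discordance, margin coverage and distance. The objective is therefore not unaddressed; what is missing is an interval or test on that comparison.

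The chosen contrast also has a rationale. MRI-only against combined volume measures how PET changes the target, and a pure size comparison is blind to location: equal volumes in different places would show no difference. This stands, and it is a reason to keep the nested contrast as an estimate beside the overlap metrics.

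A reader might infer that the planned test is nearly certain to be significant, even when PET volumes are much smaller than MRI volumes. The documents do not support that. Section 7.4 foresees PET uptake outside MRI only in some patients. Section 1.71 reports 15 of 45 biopsies from PET-avid, non-enhancing regions, but sites were chosen partly for discordance, so this is not a per-patient frequency. If PET lay wholly inside MRI in every patient, all union differences would be zero and nothing would be significant.

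**Conclusion.** The concern holds in this form: the only named and powered test in 16.82 compares volumes that are nested at GTV and CTV level, so its null is uninformative and its result cannot say whether PET uptake is larger or smaller than enhancement or FLAIR. This follows from 7.52 and 16.82 without numerical assumptions and does not depend on the Boolean operator.

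The chance of a significant result is not derivable from the documents. Under the assumed model it runs from 5-8% to about 97-99% as the share of patients with PET outside MRI goes from 15% to 100%. Near-certainty is one end of that range.

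The endpoint is correlative and has no bearing on the primary endpoint, its decision rule or the sample size. The change should be made, but the trial does not depend on it.

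**What to change.** In 16.82:

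- Make the inferential analyses for 2.31 the paired comparisons GTV_PET vs GTV_MRI and GTV_PET vs T2_FLAIR_NCET, each with a confidence interval.
- Name one primary T/N threshold in advance and use the other as a sensitivity analysis.
- Use the Wilcoxon signed-rank test. Use log volume only if no contour is empty, since the log of zero is undefined.
- Keep MRI-only vs combined volume as an estimate of added (or removed) volume with a confidence interval, beside the planned overlap and discordance metrics.
- Attach the power and effect size to GTV_PET vs GTV_MRI, recalculated for the test chosen.

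In 7.52, state the Boolean operator for GTV_high so that the direction of nesting is explicit.

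The cost is wording only, because all three contours are already planned. The downside is that the MRI-only vs combined test is no longer the headline result.

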### 16.3 Sample Size

The design to be utilized is fully described in section 0. A maximum of 20 evaluable patients will be accrued to this pilot study unless undue toxicity is

encountered. We anticipate accruing an additional 2 patients to account for ineligibility, cancellation, major treatment violation or other reasons. Maximum projected accrual is therefore 22 patients. We anticipate screening 30 patients to register a total of 22 patients necessary for study design.

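### Section 16.82 claims 80% power at effect size 0.63 with 20 patients; on the usual paired definition and normal differences, the paired t-test it names gives 76%, and 80% needs 0.66

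*Combined protocol and SAP*

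**What the plan says.** Section 16.82 (Volumetric Comparison) plans a within-patient comparison of "treatment volumes defined by MRI only and the treatment volumes defined by both PET and MRI". Its power statement is: "The analysis of volumes from 20 patients will have 80% power to detect differences in volumes with an effect size of 0.63". The same sentence names the test: a two-sided paired t-test at the 0.05 level. The section gives no definition of effect size, no SD, no within-patient correlation, and no mention of a normal approximation.

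The number 20 comes from the primary design. Section 16.3 says: "A maximum of 20 evaluable patients will be accrued". It adds two patients for ineligibility, cancellation, major violations and other reasons, and concludes: "Maximum projected accrual is therefore 22 patients".

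**The concern.** A power statement for a t-test on 20 pairs can be checked once effect size is given its usual meaning. Here the stated 80% and 0.63 do not belong together for the test that is named. With 19 degrees of freedom, the normal approximation and the t-test differ enough to matter in the second digit.

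This is the plan's only power statement for the volume comparison in goal 2.31. A reader who relies on it takes the type II error at 0.63 to be 20% when it is about 24%, and takes the detectable difference to be slightly smaller than it is.

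**Working it through.** **Inputs.** From section 16.82: n = 20 pairs, effect size d = 0.63, paired t-test, two-sided alpha 0.05, stated power 80%. From section 16.3: maximum accrual 22. Two assumptions are added because the documents are silent: d is the mean within-patient difference divided by the SD of the differences, and the differences are normally distributed.

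**1. Reproducing the plan's figure.** The stated pair comes out of the normal approximation at n = 20:

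- Detectable effect for 80% power: (z₀.₉₇₅ + z₀.₈₀)/√n = (1.960 + 0.842)/√20 = 2.802/4.472 = 0.6265, which rounds to 0.63.
- Power at 0.63: Φ(0.63 × √20 − 1.960) = Φ(2.817 − 1.960) = Φ(0.857) = 80.4%.

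**2. The test that is named.** For the paired t-test, power is the probability that a noncentral t variable with n − 1 degrees of freedom and noncentrality d√n falls outside ± t₀.₉₇₅ with n − 1 degrees of freedom.

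- Degrees of freedom: 19. Critical value: 2.093. Noncentrality: 0.63 × √20 = 2.817.
- Power: **76.2%**. A simulation of 400,000 trials with normal differences gives 76.3%.
- Shortfall: 80 − 76.2 = 3.8 percentage points.

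**3. The effect size that gives 80% power at n = 20.** Solving the same formula for d gives **0.660**. A hand approximation agrees: (t₀.₉₇₅ + t₀.₈₀)/√20 = (2.093 + 0.861)/4.472 = 0.661. Relative to the plan: 0.660/0.63 = 1.048, about 5% larger.

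**4. Can rounding or another reading rescue the figure?**

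| Variant | Power at stated effect | Effect size for 80% |
|---|---|---|
| Paired t, two-sided, n = 20, d = 0.625 (lowest value that rounds to 0.63) | 75.5% | 0.660 |
| Paired t, two-sided, n = 20, d = 0.63 | 76.2% | 0.660 |
| Paired t, two-sided, n = 20, d = 0.635 | 76.9% | 0.660 |
| Paired t, two-sided, n = 21, d = 0.63 | 78.4% | 0.643 |
| Paired t, two-sided, n = 22, d = 0.63 | 80.4% | 0.626 |
| Paired t, one-sided, n = 20, d = 0.63 | 85.8% | 0.577 |
| Normal approximation, two-sided, n = 20, d = 0.63 | 80.4% | 0.626 |

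Only the normal approximation at 20 patients and the exact t-test at 22 patients reproduce the plan's pair. Section 16.82 names neither.

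**5. Sensitivity to the definition of effect size.** Suppose instead that 0.63 is the mean difference divided by the SD of a single volume, with equal SDs and within-patient correlation r. The paired effect is then 0.63/√(2(1 − r)). At r = 0.5 this is 0.63 and power is 76%. At r = 0.55 it is 0.63/√0.90 = 0.664 and power is 80%. At r = 0.6 it is 0.63/√0.80 = 0.704 and power is 85%. The documents give no correlation, so this range is illustrative only.

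**The case against.** The strongest reply is that section 16.82 does not fix every input. Because effect size is undefined, a single-volume standardisation with r near 0.55 would make the 80% correct. That stands as a limit on the claim. It does not defend the sentence, since the plan states neither that definition nor any correlation, and the usual meaning for a paired t-test is the one used here. It is also a reason to define the term.

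A second reply is that 22 patients may be enrolled, and at 22 the figure is right. But the sentence says 20, the two extra patients are there to cover losses, and at 21 the power is still 78.4%.

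A reader might go further and infer that the volume comparison really has 76% power. The documents do not support that. The 76% depends on normal differences, a model in which about 26% of patients would have a difference of the opposite sign when d = 0.63. If the two volumes were nested within each patient, the sign could not vary and the model would fail. As an assumed illustration, gamma or lognormal differences that are always positive, with the same mean-to-SD ratio of 0.63, make the same test reject in about 97% of simulated trials of 20.

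A reader might likewise infer from nesting that the test is uninformative. The documents do not settle that either. Section 16.82 does not say at which level the volumes are compared; it says only that contours are "then expanded as noted above". Section 7.5124 sets the CTV equal to the GTV, so the only expansion in section 7.5 is the 0–2 mm PTV margin in 7.5125. With margins that may differ, nesting need not hold.

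Finally, the gap amounts to two patients, or 0.03 in effect size, on a correlative aim. That is correct, and it sets the severity.

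**Conclusion.** The power sentence in section 16.82 is wrong for the test and sample size it names, under the usual paired definition of effect size and normally distributed differences. Power at 0.63 is 76.2% (75.5% to 76.9% allowing for rounding), and 80% needs 0.66. The likely origin is the normal approximation used in place of the t-test; this is an inference from the match of the numbers, since the document does not say how the figure was obtained.

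The claim is limited to a mismatch between the stated figure and the standard calculation. It says nothing about the power the comparison will have in practice, which depends on a definition and a distribution that the plan does not give.

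Severity is minor. The sample size comes from the primary 3-month progression-free survival design (sections 16.21 and 16.3), and no decision rule uses the volume test.

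**What to change.** Replace the power sentence in section 16.82 with, for example: *With 20 patients, a paired t-test at the two-sided 0.05 level has 80% power for an effect size of 0.66 (76% for 0.63), where effect size is the mean within-patient difference in volume divided by the SD of those differences, and the differences are assumed normal.*

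If the authors meant a different standardisation, they should state it together with the within-patient correlation assumed, and recompute.

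The cost is one sentence. No patients, contours, data or analyses change. The stated figure becomes slightly less favourable.
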